#### Transportation of Thawed Vials at 2° to 8°C (35° to 46°F)

If transport at -50° to -15°C (-58° to 5°F) is not feasible, available data support transportation of one or more thawed vials for up to 12 hours at 2° to 8°C (35° to 46°F) when shipped using shipping containers which have been qualified to maintain 2° to 8°C (35° to 46°F) and under routine road and air transport conditions with shaking and vibration minimized. Once thawed and transported at 2° to 8°C (35° to 46°F), vials should not be refrozen and should be stored at 2° to 8°C (35° to 46°F) until use.

---

#### 6.2.4 PREPARATION

##### Dose Preparation

The Moderna COVID-19 Vaccine multiple-dose vials contain a frozen suspension that does not contain a preservative and must be thawed prior to administration.

Vial	Thaw in Refrigerator	Thaw at Room Temperature
Maximum 11-Dose Vial (range: 10-11 doses)	Thaw in refrigerated conditions between 2° to 8°C for 2 hours and 30 minutes. Let each vial stand at room temperature for 15 minutes before administering.	Alternatively, thaw at room temperature between 15° to 25°C for 1 hour.
Maximum 15-Dose Vial (range: 13-15 doses)	Thaw in refrigerated conditions between 2° to 8°C for 3 hours. Let each vial stand at room temperature for 15 minutes before administering.	Alternatively, thaw at room temperature between 15° to 25°C for 1 hour and 30 minutes.

Remove the required number of vial(s) from storage and thaw each vial before use following the instructions below.

After thawing, do not refreeze.

Swirl vial gently after thawing and between each withdrawal. **Do not shake.**

Do not dilute the vaccine.

The Moderna COVID-19 Vaccine is a white to off-white suspension. It may contain white or translucent product-related particulates. Visually inspect the Moderna COVID-19 Vaccine vials for other particulate matter and/or discoloration prior to administration. If either of these conditions exists, the vaccine should not be administered.

The Moderna COVID-19 Vaccine is supplied in two multiple-dose vial presentations:

- A multi-dose vial containing a maximum of 11 doses: range 10-11 doses (0.5 mL each)
- A multi-dose vial containing a maximum of 15 doses: range 13-15 doses (0.5 mL each)

Depending on the syringes and needles used for each dose, there may not be sufficient volume to extract more than 10 doses from the maximum of 11 doses vial or more than 13 doses from the maximum of 15 doses vial. Irrespective of the type of syringe and needle:

- Each dose must contain 0.5 mL of vaccine.
- If the amount of vaccine remaining in the vial cannot provide a full dose of 0.5 mL, discard the vial and contents. Do not pool excess vaccine from multiple vials.
- Pierce the stopper at a different site each time.

After the first dose has been withdrawn, the vial should be held between 2° to 25°C (36° to 77°F). Record the date and time of first use on the Moderna COVID-19 Vaccine vial label. Discard vial after 12 hours. Do not refreeze.

### 6.3 MEASURES TO MINIMIZE BIAS: RANDOMIZATION AND BLINDING

Not applicable (non-blinded, non-randomized trial)

### 6.4 STUDY INTERVENTION COMPLIANCE

Administration of the Moderna mRNA COVID-19 booster dose as part of this protocol will be documented in the medical record and there will also be a study-specific dose administration documentation form. Copies of post-administration safety assessments reflecting patient-reported symptoms/side effects on days 2-8, 15, 22, and 28 will be filed in each participant's shadow chart in CTO.

### 6.5 CONCOMITANT THERAPY

For this protocol, the only prohibited medication is daily corticosteroids at a dose equivalent to or greater than Prednisone 20 mg/day. *Intermittent* steroid dosing, including higher doses such as the weekly dexamethasone dosing used as part of typical myeloma or AL amyloidosis regimens, is permitted. In such cases, as well as for patients currently receiving potentially immunosuppressive anti-neoplastic therapy for their underlying hematologic condition, a two-week interruption in therapy before and after the booster dose of vaccine is ENCOURAGED BUT NOT REQUIRED (physician discretion).

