### 3 OBJECTIVES AND ENDPOINTS

OBJECTIVES	ENDPOINTS	JUSTIFICATION FOR ENDPOINTS
Primary		
To determine whether booster dosing with the Moderna COVID-19 vaccine can induce humoral immune responses in patients with hematologic malignancies who did not have an adequate response to prior first vaccination with any of the SARS-CoV2 vaccines authorized for use in the USA.	The primary endpoint is the observed rate of anti-SARS-CoV2 IgG antibody seroconversion (from negative to positive) measured 28 days (+/- 3 days) following a booster dose of the Moderna COVID-19 vaccine.	The described assay measures antibodies against the SARS-CoV2 spike protein, which is what the Moderna vaccine is designed to induce. This is a commercially available assay which is already in use at the Karmanos Cancer Center and Detroit Medical Center.
Secondary		
1. To determine whether booster dosing with the Moderna COVID-19 vaccine is safe in patients with multiple myeloma, AL amyloidosis, or other hematologic malignancies.  2. To compare the humoral immune responses between the patients who had a WEAK POSITIVE RESPONSE to prior vaccine (Cohort 3) vs. those with NO RESPONSE to prior vaccination (Cohorts 1 and 2).  3. To descriptively summarize clinical and immune characteristics which contribute to likelihood of	1. AEs and SAEs observed in participants, determined according to daily phone calls or video chats for 1 week following vaccine administration, and then weekly after that until 4 weeks after vaccination (Pts will also be examined 4 weeks after vaccination).  2. Humoral immune responses measured 28 days (+/- 3 days) following a booster dose of the Moderna COVID-19 vaccine.  3.a. Clinical characteristics of enrolled participants, including treatment history, disease, status, or presence	This is an early experience with booster dosing using the Moderna COVID-19 vaccine. Though new AEs/SAEs are not expected, it is important to document the safety of this intervention.  Clinical factors related to disease or immune status may be associated with likelihood of responding to booster

OBJECTIVES	ENDPOINTS	JUSTIFICATION FOR ENDPOINTS

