### 5 STUDY POPULATION

#### 5.1 INCLUSION CRITERIA

In order to be eligible to participate in this study, an individual must meet all of the following criteria:

1. Provision of signed and dated informed consent form
2. Stated willingness to comply with all study procedures and availability for the duration of the study
3. Male or female, aged 18 years of age or older
4. Previously diagnosed with MM/AL amyloidosis (Cohorts 1 or 3) or other hematologic malignancy (Cohorts 2 or 3).
5. Previously received any one of the available COVID-19 vaccines (between 4 and 36 weeks prior to enrollment)
6. Anti-SARS-CoV2 IgG antibody titer of results less than 1.0 units (Cohorts 1 and 2), or 1.0-1.99 units (Cohort 3). Antibody titers will be measured within 14 days of enrollment.
7. If currently receiving potentially immunosuppressive anti-neoplastic therapy for their underlying hematologic condition, a two-week interruption in therapy before and after the booster dose of vaccine is ENCOURAGED BUT NOT REQUIRED (physician discretion).

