### 5.3 LIFESTYLE CONSIDERATIONS

Patients who are diagnosed with an acute SARS-CoV2 infection in the post-vaccine follow-up period (i.e., between the vaccine and the serologic testing for response to vaccine) will be considered non-evaluable for the primary endpoint of the trial.

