## 8 STUDY ASSESSMENTS AND PROCEDURES

### 8.1 EFFICACY ASSESSMENTS

**Please refer to the Study Calendar (Section 1.3) for a complete list of protocol-related assessments.**

A blood specimen collection will be performed on day 28 (+/- 3 days) after the administration of the booster dose of the Moderna mRNA COVID-19 vaccine. An anti-SARS-CoV2 IgG Ab titer will be measured using this sample. This is the primary efficacy assessment being performed as part of this trial.

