## 9.4 ANALYSIS PLAN

### 9.4.1 EFFICACY ANALYSES

Within each cohort, all participants who receive the protocol-specified booster dose of the Moderna COVID-19 vaccine and then have blood sampled within the protocol-specified time window will be included in the efficacy analysis ("efficacy analysis datasets"). There will be an efficacy dataset for each cohort individually.

For the primary and second secondary objectives, the response rate (RR), which is the primary endpoint, will be summarized with frequency, percentage and its associated 2-sided 90% confidence interval (i.e., 1-sided 95% confidence interval), separately by each cohort and by the combined cohort (Cohort 1+2).

For the second secondary objectives, the Fisher's exact test will be used to compare between Cohort 3 vs. Cohort 1+2.

For the third secondary objective, the patient demographic, clinical, and immune characteristics will be summarized by mean, median, standard deviation, range, confidence interval for continuous variables and by frequency, percentage and its associated confidence interval for categorical variables.

As an exploratory analysis, univariable logistic models will be used to explore the associations between patient characteristics and the treatment response.

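### Participants who acquire anti-spike IgG from a source other than the booster stay in the efficacy set, and any whose titre reaches the cut-off as a result count as booster responses

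*Combined protocol and SAP*

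**What the plan says.** Section 6.5 (Concomitant Therapy) is explicit about its scope: "For this protocol, the only prohibited medication is daily corticosteroids at a dose equivalent to or greater than Prednisone 20 mg/day". None of the five exclusion criteria in Section 5.2 mentions antibody products, immunoglobulin or a further vaccine dose.

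The endpoint is serological. The table in Section 3 states: "The described assay measures antibodies against the SARS-CoV2 spike protein". Nothing in the documents says that the assay can tell antibody made by the patient from antibody given to the patient. On the baseline value, Section 5.1 says: "Antibody titers will be measured within 14 days of enrollment". The calendar in Section 1.3 shows no repeat titre on Day 1. On the outcome value, Section 8.1 says: "A blood specimen collection will be performed on day 28 (+/- 3 days) after the administration of the booster dose".

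Section 9.4.1 puts into each cohort's efficacy set "all participants who receive the protocol-specified booster dose of the Moderna COVID-19 vaccine and then have blood sampled within the protocol-specified time window". One exception appears elsewhere, in Section 5.3: "Patients who are diagnosed with an acute SARS-CoV2 infection in the post-vaccine follow-up period", meaning before the response serology, "will be considered non-evaluable for the primary endpoint of the trial".

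**The concern.** The primary analysis attributes a Day 28 titre at the cut-off to the booster. There is no control arm from which antibody of other origin could be estimated and subtracted. Section 5.3 already accepts the principle that a participant with a competing source of antibody should not count towards the primary endpoint, but it applies that principle to infection alone.

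Each cohort is judged on 6 responders out of 52, so a small number of misattributed responses could matter. The same classification feeds the comparison of Cohort 3 with Cohorts 1 and 2, and the exploratory logistic models of response. If use of an antibody product were related to immunoparesis, a characteristic listed in endpoint 3.a, those models could also be distorted.

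**Working it through.** **1. Which exposures do the rules cover?** The interval at issue runs from the screening titre (as early as Day -14) to the Day 28 sample (as late as Day 31), about 45 days.

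| Exposure | Rule that applies | Covered? |
|---|---|---|
| Antibody product given for an acute infection diagnosed after the booster | 5.3, non-evaluable | Yes |
| Non-study vaccine dose between screening and enrolment | 5.1 criterion 5 (prior vaccination 4 to 36 weeks before enrolment) | Arguably |
| Non-study vaccine dose after enrolment | 7.2 allows discretionary withdrawal on listed grounds; this is not named | No |
| Preventive anti-spike antibody, convalescent plasma or immunoglobulin between the screening titre and Day 28 | None | No |

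The calendar schedules concomitant medication review at screening and Day 28, so these products could be recorded. No analysis rule uses the record.

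**2. Reproduce the design (Section 9.3).** Inputs: n = 52 per cohort, reject at 6 or more responders, p0 = 5%, p1 = 15%, 1-sided alpha 5%, power 80%.

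- P(Bin(52, 0.05) ≥ 6) = 0.0445
- P(Bin(52, 0.15) ≥ 6) = 0.812

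The stated design is reproduced.

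**3. Illustration A: other sources add to a 5% booster rate.** Assume that c participants cross the cut-off for another reason and that the other 52 − c respond at 5%. The chance of declaring success is P(Bin(52 − c, 0.05) ≥ 6 − c).

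- c = 0: 0.045
- c = 1: P(Bin(51, 0.05) ≥ 5) = 0.110
- c = 2: P(Bin(50, 0.05) ≥ 4) = 0.240

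As an assumed exposed fraction f, all crossing the cut-off, the apparent rate is 0.05 + 0.95f:

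- f = 1%: rate 0.0595, probability 8.7%
- f = 2%: rate 0.0690, probability 14.7%
- f = 5%: rate 0.0975, probability 39.7%

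**4. Illustration B: other sources lie within the 5%.** Section 9.3 frames the null as patients reaching a higher titre spontaneously, which can be read as an allowance for rises that the booster did not cause. If the booster does nothing and other sources supply the whole background, the chance is P(Bin(52, f) ≥ 6):

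- f = 1%: 0.001%
- f = 2%: 0.06%
- f = 5%: 4.5%

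**5. Power if exposed participants become non-evaluable.** With p = 15% and the threshold kept at 6:

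- none lost, or losses replaced to n = 52: 0.812
- one not replaced (n = 51): 0.797
- two not replaced (n = 50): 0.781
- five not replaced (n = 47): 0.727

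**The case against.** The best counter-argument is that no harm has been shown. A false response needs a product given in the interval and enough anti-spike IgG in it to bring the Day 28 titre to the cut-off. The documents give neither the frequency of use nor the anti-spike content, and they do not mention immunoglobulin replacement at all. That patients with hypogammaglobulinemia would receive it is an inference. Illustration A also assumes that every exposed patient crosses the cut-off, on top of a full 5% booster rate; Illustration B shows no inflation up to 5% exposure. These points stand and limit what can be said about size.

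It is also fair that some protection exists. A patient on regular immunoglobulin that already raises anti-spike IgG enough would exceed the eligibility limits at screening, so the open cases are products started, changed or timed differently afterwards. The first two rows of the table above are wholly or arguably covered.

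Finally, concomitant medications and quantitative immunoglobulins are collected at screening and Day 28, and paired correlative samples are planned. That makes a later sensitivity analysis feasible. It does not supply a rule fixed in advance, and in an open-label trial a case-by-case decision made after titres are known would be open to question.

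**Conclusion.** The gap is real. Read together, Sections 6.5, 5.3 and 9.4.1 keep in the efficacy set participants with another source of anti-spike IgG, and those lifted to the cut-off count as booster responses. This is a wrong classification under the plan's own stated rule, and it departs from the principle applied in 5.3.

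A reader might infer more: that everyone given such a product would be scored as a responder, or that the type I error is in fact 11% or 24%. The documents support neither. Those figures hold only under Illustration A. Under the background reading of the null, the error does not exceed 4.5% for exposure up to 5%. The wording of 9.3 does not settle which reading is meant, and the actual bias is unknown. The point should be fixed, but it does not show the primary analysis to be invalid.

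**What to change.** In Section 9.4.1, cross-referenced from 5.3 and 6.5, state that a participant is non-evaluable for the primary endpoint and the second secondary objective, as 5.3 provides for infection, after either of the following:

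- a preventive anti-spike antibody, convalescent plasma or immunoglobulin infusion between the screening titre and the Day 28 sample;
- a non-study COVID-19 vaccine dose after enrolment.

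Such participants stay in the toxicity dataset. Add two sensitivity analyses, one counting them as non-responders and one including them as observed. Record product and date through the concomitant medication review already in the calendar. This changes classification only; no restriction on care is proposed.

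The cost is a short addition to 9.4.1, a CRF prompt and a few non-evaluable participants. The power loss is small if one or two are not replaced (0.797 or 0.781), and replacement within the allowance of 5 per cohort in 9.3 restores 0.812. Replacement there is conditional, so the text should say whether these participants qualify. Exclusions may fall mainly on participants with immunoparesis and may remove some genuine responders. The as-observed analysis would show whether that matters.

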#### 6.5.1 RESCUE MEDICINE

Standard medications used for the management of a hypersensitivity reaction (in the unlikely event such a reaction occurs) are permitted, to be administered according to the discretion of the treating physician.

## 7 STUDY INTERVENTION DISCONTINUATION AND PARTICIPANT DISCONTINUATION/WITHDRAWAL

### 7.1 DISCONTINUATION OF STUDY INTERVENTION

If a clinically significant finding is identified after participants are enrolled and treated on study, the investigator or qualified designee will determine if any change in participant management is needed. Any new clinically relevant finding will be reported as an adverse event (AE).

### 7.2 PARTICIPANT DISCONTINUATION/WITHDRAWAL FROM THE STUDY

Participants are free to withdraw from participation in the study at any time upon request.

An investigator may discontinue or withdraw a participant from the study for the following reasons:

- Significant study intervention non-compliance
- If any clinical adverse event (AE), laboratory abnormality, or other medical condition or situation occurs such that continued participation in the study would not be in the best interest of the participant
- Documented SARS-CoV2 infection
- If the participant meets an exclusion criterion (either newly developed or not previously recognized) that precludes further study participation
- Participant unable to return for post vaccination assessment at 28 days (+/- 3 days) after vaccination. NOTE: patients who miss this window but are able to return to complete required assessments may be able to remain on trial (treating physician must discuss with the PI).

The reason for participant discontinuation or withdrawal from the study will be recorded on the Case Report Form (CRF). Subjects who sign the informed consent form and are enrolled but do not receive the study intervention may be replaced. Subjects who sign the informed consent form, and receive the study intervention, and subsequently withdraw, or are withdrawn or discontinued from the study, will be replaced.

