## 1.2 SCHEMA

### ***Flow diagram***

### 1.3 SCHEDULE OF ACTIVITIES (STUDY CALENDAR)

Procedures	Screening/Consenting Day -14 to -1	Enrollment/Baseline Visit 1, Day 1	Days 2-8, 15, 22 (+/- 1 day) Phone/Text/Email	Study Visit 2 Day 28 +/- 3 days
Informed consent	X			
Demographics	X			
Medical history update	X			X
Administer vaccine dose		X		
Concomitant medication review	X			X
Physical exam	X			X
Vital signs	X	X		X
Height	X			
Weight	X			X
Performance status f	X			X
Hematology a	X			X
Serum chemistry b	X			X
Cardiac Biomarkers e	X		(X) d	X
Coagulation testing c	X			
Anti-SARS-CoV2 IgG Ab titer	X			X
Patient-reported AE assessment		X	X---X	X
Correlative blood sample collection	X			X

a. CBC with diff  
b. standard CMP, uric acid, magnesium, phosphorus, LDH, quantitative immunoglobulins (IgG, IgA, IgM)  
c. PT/INR, PTT, fibrinogen  
d. only if patient reports chest pain, palpitations, shortness of breath, or other symptoms suggesting cardiac etiology  
e. hsTrop I and BNP  
f. See Appendix 1: ECOG Performance Status

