#### 5.2 EXCLUSION CRITERIA

An individual who meets any of the following criteria will be excluded from participation in this study:

1. Daily corticosteroids at a dose equivalent to Prednisone 20 mg/day or greater during the period two weeks before enrollment to the trial. *Intermittent* steroid dosing at or above this level is permitted (i.e., weekly dexamethasone dosing as part of myeloma therapy)
2. History of previous severe reaction to any available COVID-19 vaccine (defined as any Grade 3 or higher reaction)
3. Febrile illness within 3 days of booster dosing.
4. Documented SARS-CoV2 infection within 2 weeks of enrollment.
5. Less than 3 months post-autologous or allogeneic stem cell transplant (NOTE: transplant between initial standard vaccine administration and enrollment is NOT otherwise grounds for exclusion from participation).

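### Section 7.2 allows discretionary withdrawal and replacement of already-dosed participants who newly meet an exclusion criterion, so decisions made after the single injection can change who is in the primary efficacy set

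*Combined protocol and SAP*

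**What the plan says.** - **Withdrawal (7.2).** The list of reasons opens with "An investigator may discontinue or withdraw a participant from the study for the following reasons". One entry is "If the participant meets an exclusion criterion (either newly developed or not previously recognized) that precludes further study participation". No entry separates the time before the injection from the time after it.
- **Replacement (7.2).** Participants who consent, receive the vaccine and "subsequently withdraw, or are withdrawn or discontinued from the study, will be replaced". Withdrawal after dosing is therefore foreseen.
- **Replacement (9.3).** Here the rule is conditional. Non-evaluable patients are replaced only where that is needed to settle whether a cohort meets the primary endpoint. At most five extra patients per cohort are expected, which gives the ceiling of 57 × 3 = 171.
- **Efficacy set (9.4.1).** It consists of participants in a cohort who receive the booster and "have blood sampled within the protocol-specified time window will be included in the efficacy analysis". Section 9.4.2 defines an all-dosed set, but for toxicity only.
- **Exclusion 3 (5.2).** "Febrile illness within 3 days of booster dosing", with no statement of before or after. Exclusion 1, by contrast, fixes its window before enrollment.
- **Timing (1.3).** The vaccine is given at "Enrollment/Baseline Visit 1, Day 1", so enrollment and dosing fall on the same day.

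**The concern.** The intervention is a single injection. Once it has been given, withdrawal by the investigator stops no treatment. It ends only the remaining safety contacts and the Day-28 sample on which the primary endpoint rests. A dosed participant who is withdrawn leaves the efficacy set and is replaced. The same participant, left on study and sampled in the window, is counted. In an open-label trial that choice is made by someone who knows what has happened to the patient since the dose.

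If the reasons for withdrawal are related to antibody response in either direction, the response rate in the analysed 52 no longer estimates the rate among patients given the booster. The decision rule has little slack, so a few replacements in one cohort can matter.

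**Working it through.** **1. The plan's own design.** Inputs from 9.3: p0 = 5%, p1 = 15%, one-sided alpha 5%, power 80%, n = 52 per cohort, reject at six or more responders. The exact binomial gives:

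- error: P(X ≥ 6 | 52, 0.05) = 0.0445
- power: P(X ≥ 6 | 52, 0.15) = 0.812

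The smallest n that meets both targets is 52. The stated design reproduces and is not in question.

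**2. The path through the text.** Take one dosed participant who newly meets an exclusion criterion before Day 28.

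| Investigator's choice | Day-28 sample | In 9.4.1 set | Replaced under 7.2 |
|---|---|---|---|
| Leaves the participant on study | yes, if in window | yes | no |
| Withdraws the participant | no | no | yes |

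The text permits both rows, so membership of the set can depend on a discretionary act after dosing.

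**3. Bound if all those replaced are non-responders.** Let d be the number dosed, of whom d − 52 non-responders are withdrawn and replaced. Six responders among the analysed 52 are then six responders among d dosed, so the error is P(X ≥ 6 | d, 0.05).

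| Dosed (d) | Replaced | One-sided error |
|---|---|---|
| 52 | 0 | 0.0445 |
| 53 | 1 | 0.048 |
| 54 | 2 | 0.052 |
| 55 | 3 | 0.056 |
| 56 | 4 | 0.060 |
| 57 | 5 | 0.065 |

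The 5% level is passed at two replacements. The last row is the per-cohort ceiling in 9.3.

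**4. The other direction.** Let f be the share of dosed participants removed, and RR the response rate in those removed divided by the rate in those kept. The rate among those kept is p / (1 − f + f·RR). The documents give neither quantity. For illustration take f = 7.0%.

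- RR = 2, p = 0.15: 0.15 / 1.07 = 0.140, power 0.755. With p = 0.05: 0.05 / 1.07 = 0.047, error 0.034.
- RR = 3, p = 0.15: 0.15 / 1.14 = 0.132, power 0.696.
- RR = 1: no change (error 0.0445, power 0.812).
- RR = 0, p = 0.05: 0.05 / 0.93 = 0.054, error 0.059.

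The sign of the effect depends entirely on RR.

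**The case against.** The strongest reply is that the entry was meant for the period before dosing and carries its own limit. Screening runs from Day −14 to Day −1, so a criterion can newly arise between consent and injection, and the entry has a natural use there. It also requires that the criterion rule out further participation. After one injection only remote contacts and one visit remain, which few events would rule out. Withdrawal is optional, and anyone sampled in the window is kept. All of this stands, and it is why the point is that decisions after dosing can change the set, not that they will. It does not close the gap, because 7.2 states no pre-dose limit and provides for replacing participants withdrawn after the dose.

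A reader might infer more from exclusion 3: that ordinary vaccine fever will remove several patients per cohort. The documents do not support that. Section 5.4 treats febrile illness as a reason for screen failure with possible rescreening, and 10.1.6 treats fever after the dose as an adverse event to be collected and followed up. The fever rates in 2.3.1 would mean 52 × 2/38 = 2.7 to 52 × 0.070 = 3.6 febrile participants per cohort at the 0.25 mL booster rates, or 52 × 0.100 = 5.2 to 52 × 0.174 = 9.0 at the second-dose rates. Those are fevers over seven days, not withdrawals, and exclusion 3 names three days. If fever did go with a stronger vaccine response, removing febrile patients would lower the observed rate, so fever cannot be used to support the non-responder bound.

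A reader might also think that daily steroids started after the dose trigger the entry. They do not. Exclusion 1 covers the two weeks before enrollment, and the limit in 6.5 is a concomitant-medication rule, not an exclusion criterion.

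Finally, the plan openly prespecifies a response-evaluable set, which is a common phase 2 choice. That is fair. It makes an all-dosed table a supplement and not a replacement for the primary analysis.

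**Conclusion.** The point holds as a gap in wording with a consequence for the primary analysis. Sections 7.2 and 9.4.1 together let discretionary decisions after dosing determine membership of the efficacy set, and no all-dosed efficacy analysis is planned that would show the effect.

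The size and direction of any bias are unknown. The rise in error from 0.0445 to 0.052 with two replacements and 0.065 with five is a bound. It assumes that everyone replaced is a non-responder and that the five-patient allowance is kept. If those removed respond better than average, the error falls and power is lost instead. It would be wrong to conclude that the trial's error rate is inflated or that the sample size is mistaken: if dosed participants stay in the set, the design keeps its error of 0.0445 and power of 0.812. The change is worth making because it is cheap and removes a source of selection that the results could not otherwise rule out.

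**What to change.** - **7.2:** State that exclusion criteria are applied up to dosing. A dosed participant who later meets one stays in follow-up for the Day-28 titre and safety contacts, where the participant agrees. Leave the separate provision for withdrawal in the participant's best interest as it is.
- **5.2 item 3:** State the direction of the three-day window and reconcile it with 5.4 and 7.2.
- **7.2 and 9.3:** Reconcile the two replacement rules, unconditional in one and conditional in the other.
- **9.4.1:** Add one supportive analysis per cohort of all dosed participants, with a missing Day-28 titre counted as non-response and the exact binomial test at the number dosed. Say how participants made non-evaluable under 5.3 for post-dose infection are handled in it. Report by reason the dosed participants left out of the efficacy set.

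The cost is wording in four sections and one extra table. No visit is added and n = 52 stands. The supportive response rate will be slightly lower. Its test will also be stricter where more are dosed: six responders no longer suffice from 54 dosed, and at 57 the threshold of seven has an error of 0.023.
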